3.4 Other imaging variables

Result of MRI assessments and thorax/abdomen CT scan will be presented in listings. Overall response from the BM assessment according to CNS RECIST v1.1, as captured on the pCRF, from the brain MRI after 3 weeks of multiple administrations will be summarised. Overall response from the extra-cranial tumour assessment according to RECIST v1.1, as captured on the pCRF, from thorax/abdomen CT after 3 weeks of multiple administrations will also be summarised.

CCI

3.5 Compliance to study treatment (imaging phase)

The administration of study treatment will be recorded in the appropriate sections of the paper case report form (pCRF). For the imaging phase, when the patients are not resident in the clinic, patients will report any self-administered medications along with date and time of each administration in the Patient Diary Card. For the imaging phase, when patients are at the study centre, compliance will be assured by supervised administration of IP by the Investigator or his/her delegate and recorded in the pCRF.

Study centre pharmacy staff will make tablet counts at regular intervals during treatment. For the imaging phase, diaries will be reviewed and tablet counts performed at each outpatient visit and at check-in on Day 29.

Compliance will be assessed by the tablet count, and the information will be recorded in the appropriate sections of the pCRF. After the tablet count has been performed, the remaining capsules will not be returned to the patient but will be retained by the study centre until reconciliation is completed by the study monitor.

Estimated overall compliance will be derived using the following formula:

$$\text{Overall Compliance} = \frac{\text{Total number of tablets dispensed} - \text{Total number of tablets returned}}{\text{Last date of tablets returned} - \text{First date of tablets dispensed}} \times 100$$

where, 'total number of tablets dispensed' refers to all dispensed tablets over multiple time periods and 'total number of tablets returned' refers to all returned tablets over multiple time periods.

4. ANALYSIS METHODS

4.1 General principles

Derivation of the quantitative PET imaging parameters for [¹¹C]osimertinib will be the responsibility of Karolinska Institute, Department of Clinical Neuroscience, **PPD**, Solna, Sweden. Pharmacokinetic analysis and derivation of PK parameters will be the responsibility of AstraZeneca. Statistical summaries and analyses of data will be performed by IQVIA under the direction of the Biostatistics Group, AstraZeneca using SAS® Version 9.4 or higher and, where appropriate, additional validated software.

The clinical database will close and the data will be reported in a CSR when the last patient either completes the 30-day (± 7 days) follow-up visit after their last administration in the imaging phase, or discontinues from the study, whichever comes first.

All individual data as recorded in the final study database will be provided by IQVIA Data Management for analysis.

The treatments will be labelled in relevant summaries and listings as:

- “Osimertinib 80 mg”
- “[¹¹C]osimertinib”

and defined as follows:

- “Osimertinib 80 mg”: 80 mg osimertinib film-coated oral tablets, manufactured by AstraZeneca
- “[¹¹C]osimertinib”: radiolabelled [¹¹C]osimertinib, manufactured *ex tempore* by the positron emission tomography centre, Radiochemistry Laboratory at the Karolinska Institutet, **PPD**, Solna, Sweden

For qualitative variables, the population size (N for sample size and n for available data) and the percentage (of available data) for each class of the variable will be presented.

Quantitative variables will be summarised using descriptive statistics, including n, arithmetic mean, standard deviation (SD; calculated using untransformed data), median, minimum (min), and maximum (max) values. Geometric mean and coefficient of variation will be included for exposure parameters, as applicable.

Where appropriate, safety data will be summarised by scheduled visit.

4.2 General variables

4.2.1 Study day definitions

For data summaries, Study Day 1 is defined as the date of first IV microdose administration of [¹¹C]osimertinib. For visits (or events) that occur on or after Study Day 1, study day is defined as (date of visit [event] – date of first IV microdose administration of [¹¹C]osimertinib + 1).

For visits (or events) that occur prior to Study Day 1, study day is defined as (date of visit [event] – date of first IV microdose administration of [¹¹C]osimertinib). There is no Study Day 0.

For listings (such as for AEs) that include the derivation of “days since last dose”, this is defined as (event date – date of last dose). Events that occur on the same day as the last dose of study drug will therefore be described as occurring zero days from the last dose of study drug.

4.2.2 Visit windows

For summaries of vital signs, laboratory data, ECG, etc., assessments will be assigned to calculated visit windows (using study day).

The time windows should be exhaustive so that data recorded at any time point has the potential to be summarised. Inclusion within the visit window should be based on the actual date and not the intended date of the visit. For summaries at a subject level, all values should be included, regardless of whether they appear in a corresponding visit based summary, when deriving a subject level statistic such as a maximum.

The windows for the visits following baseline (including scheduled visits) will be constructed in such a way that the upper limit of the interval falls half way between the two visits.

For summaries showing the maximum or minimum values, the maximum/minimum value recorded on treatment will be used (regardless of where it falls in an interval). Values from scheduled and unscheduled visits will be included. Listings should display all values contributing to a time point for a subject; they should also highlight the value for that subject that was used in the summary table, wherever feasible.

For visit-based summaries, if there is more than one value per subject within a visit window then the closest to the planned study day value should be summarised, or the earlier in the event the values are equidistant from the planned study day. The visit will be missing if no assessment was reported within the specified visit window around the planned study day.

4.2.3 Handling missing data

In general, other than for partial dates, missing data will not be imputed and will be treated as missing.

4.2.3.1 Imputation of partial dates

Concomitant medication and adverse events start dates

- If year is missing (or completely missing), do not impute
- If (year is present and month and day are missing) or (year and day are present and month is missing), impute as January 1st
- If year and month are present and day is missing, impute days as first day of the month

Concomitant medication and adverse events end dates

- If year is missing (or completely missing), do not impute
- If (year is present and month and day are missing) or (year and day are present and month is missing), impute as December 31st, unless this is after the date of death in which case date of death will be used instead
- If year and month are present and day is missing, impute day as last day of the month, unless this is after the date of death in which case date of death will be used instead

In addition, for AEs and CMs if, for a partial start date, the start date could (when also considering the end date) potentially be on the first study medication date, the start date will be imputed with the first study medication date to assume a “worst case” scenario; e.g. AE from UNK-Feb-2014 to 23-Mar-2014 with first study medication date 21-Feb-2014, then the AE start date will be imputed to 21-Feb-2014.

4.2.4 Imputation rules for lab values outside of quantification range

Lab values below the lower limit of quantification (LLoQ) that are reported as “<LLoQ” or “≤LLoQ” in the database will be imputed by $LLoQ \times 0.99$ for analysis purposes. The original value will be listed.

Lab values above the upper level of quantification (ULoQ) that are reported as “>ULoQ” or “≥ULoQ” in the database will be imputed by $ULoQ \times 1.01$ for analysis purposes. The original value will be listed.

4.3 Analysis methods

4.3.1 Screening and demographic measurements

Disposition of patients

A summary table will be presented specifying the number of patients enrolled, who received treatment, who completed the study, and who terminated prematurely. Data will be summarised across all patients.

In addition, the number of patients included in safety analysis set as well as important protocol deviations will also be summarised within separate tables. These data will be summarised across all patients.

Demographic data

Descriptive statistics will be presented for age, height, weight and BMI. In addition, frequencies and percentage of patients will be tabulated for the categorical variables age group (< 40, >=40 up to 50, >=50 up to 65, and >=65 years), smoking status (never, former, and current), sex and ethnic group. Data will be summarised across all patients.

Concomitant medication

Prior medications, concomitant and post-treatment medications are defined based on imputed start and stop dates as follow:

- Prior medications are those taken prior to study treatment with a stop date prior to the date of first IV microdose administration of [¹¹C]osimertinib
- Concomitant medications are those with a stop date on or after the date of first IV microdose administration of [¹¹C]osimertinib (and could have started prior to or during treatment)
- Post-treatment medications are those with a start date after the date of last IV microdose administration of [¹¹C]osimertinib or oral osimertinib, whichever is later

Concomitant medications will be summarised by the coded terms in separate tables per whether the medication is allowed or disallowed based on Appendix C of the clinical study protocol. For inclusion in concomitant medication summaries, incomplete medication start and stop dates will be imputed as detailed in Section 4.2.3.1. The number of patients receiving a medication will be summarised across all patients. A patient is only counted once even if they receive the medication more than once. For detailed information regarding concomitant treatments see Section 7.7 of the protocol.

Other baseline data

Other demographic and baseline data will be listed and/or summarised (as appropriate) across all patients. These data will include nicotine usage, medical and surgical history, past cancer treatments and radiotherapy, performance status, serology, and results from pregnancy test, follicle-stimulating hormone assessment, luteinising hormone assessment, and physical examination.

4.3.2 Important protocol deviations

Important protocol deviations are described in Section 2.2. A listing detailing the important protocol deviations for each enrolled patients will be presented. Minor protocol deviations, not expected to affect the treatment outcome, will not be included in this listing.

A table summarizing the important protocol deviations, along with the number and percentage of patients overall will be presented (based on the safety analysis set).

4.3.3 Safety parameters

Safety variables

All safety analyses will be performed on the safety analysis set.

Treatment Exposure

Treatment exposure data will be listed and summarised. Total exposure time and actual exposure time will be summarized using descriptive statistics for oral osimertinib exposure while frequency count of subjects taking number of doses (1, 2 or 3) will be presented for [¹¹C]osimertinib exposure.

Adverse Events

All AEs will be listed for each patient, and TEAEs will be summarised.

The following summary tables will be presented across all patients.

- Summary of number (%) of patients who had at least one AE in any category (Any AE, any causally related AE, any AE of CTCAE grade 3 or higher, any causally related AE of CTCAE grade 3 or higher, any AE with outcome = death, any causally related AE with outcome=death, any SAE (including events with outcome = death), any causally related SAE (including events with outcome = death), any SAE leading to discontinuation of investigational product (IP ie, osimertinib), any causally related SAE leading to discontinuation of IP, any AE leading to discontinuation of IP, any causally related AE leading to discontinuation of IP, any other significant AE, any other causally related significant AE (OAE)).
- Summary of number (%) of patients who had at least 1 AE by system organ class and preferred term presented by maximum reported CTCAE grade.
- Summary of number (%) of patients who had at least 1 AE with CTCAE grade 3 or higher by system organ class and preferred term.
- Summary of number (%) of patients who died and a listing of deaths.
- A listing of key information for SAEs, and a listing of key information for SAEs with outcome other than death will be presented.
- A listing of key information for AEs leading to discontinuation of IP will be presented.
- Summary of number (%) of patients who had an AE which started prior to study treatment or more than 30 days after last dose of study treatment, by system organ class and preferred term.

Clinical laboratory variables (haematology, clinical chemistry, coagulation and urine analysis)

All laboratory safety data, incorporating haematology, clinical chemistry, coagulation and urine analysis will be listed for each patient with values outside the standard reference ranges indicated in the listings.

Observed and change from baseline values will be summarised by scheduled time point.

Vital signs (pulse and BP), body temperature and weight

Pulse rate, systolic and diastolic BP, body temperature and weight will be listed by patient and summarised for observed and change from baseline by scheduled time point.

Electrocardiogram, physical examination and echocardiogram/MUGA

Electrocardiogram variables (heart rate, RR, PR, QRS, QT, and QTcF intervals) will be listed individually by patient and summarized for observed and change from baseline by scheduled time points. QTc outliers are defined as QTcF values following dosing that are greater than 450 ms or are increases from baseline greater than 30 ms. QTcF outliers will be highlighted in the data listings and summarised using the following categories:

- Values >450 ms, >480 ms, >500 ms
- Increase from baseline of >30 ms, increase from baseline of >60 ms, increase from baseline of >90 ms
- Values >450 ms and increases of >30 ms, values >500 ms and increases of >60 ms.

The number and percentage of patients who meet the ECG outlier criteria at any assessment post-date of first administration of microdose of [¹¹C]osimertinib will be summarised.

Overall ECG evaluation will be summarised using shift tables summarising the change from baseline to last on-treatment observation across all patients.

The results of physical examination and echocardiogram conducted during the study will be presented in listings. Left Ventricular Ejection Fraction (LVEF) data from echocardiogram will be summarised.

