4. STUDY PLAN AND TIMING OF PROCEDURES

The overall Study Plan is provided in Table 1 for the imaging phase.

Table 1 Study Plan and timing of procedures

Activity	Screening period	Study period					Follow up
		PET1	PET2	Clinical Visit 2	Clinical Visit 3 and PET3	MRI2	
Visit ^a	1 ^{a,b}	2	3 ^c	4 ^d	5 ^e	6	7 ^{w,x}
Day (window)	-28 to -1 day before dosing	1	2 (within 6 days)	14 (± 2 days)	+25 (± 4 days)		
Obtain informed consent and/or consent for pharmacogenetics	X						
Confirm eligibility	X						
Demographics & baseline characteristics	X ^b						
Inclusion/exclusion criteria	X	X					
Relevant medical and surgical history (including smoking status)	X						
Ophthalmic examination ^f	X						
WHO performance status	X						
Physical examination	X			X	X		X
Brain MRI	X ^{g,h}				X ^h	X ^h	
Allen's test ⁱ	X	X	X		X		
Thorax/abdomen CT	X					X ^e	
Resting standard 12-lead ECG	X ^b	X	X	X	X		
Echcardiography (ECHO/MUGA ^j)	X	X ^j	X ^j	X ^j	X ^j	X ^j	X ^j
HBV, HCV and HIV serology	X						
Weight and height	X ^k				X		
Vital signs	X	X	X	X	X		X
Laboratory tests (haematology, clinical chemistry, coagulation) ^l	X	X	X	X	X		X
Urine analysis ^l	X	X	X	X	X		
Serum or urine pregnancy test ^m (LH, FSH)	X	X	X	X	X		X
Review current medications	X ⁿ	X ⁿ	X ⁿ	X ⁿ	X ⁿ		X
Blood sampling for osimertinib PK			X ^o		X ^o		
CSF ^p	X				X		

Table 1 Study Plan and timing of procedures

Activity	Screening period	Study period					Follow up
		PET1	PET2	Clinical Visit 2	Clinical Visit 3 and PET3	MRI2	
Visit ^a	1 ^{a,b}	2	3 ^c	4 ^d	5 ^e	6	7 ^{w,x}
Day (window)	-28 to -1 day before dosing	1	2 (within 6 days)	14 (± 2 days)	+25 (± 4 days)		
Tissue and blood sampling for EGFR mutations/resistance mechanisms ^g	X ^q						X ^q
Blood sampling for ctDNA/exosomal DNA/RNA/protein	X	X	X		X		X
Arterial catheter placement ^r , and arterial blood sampling for [¹¹ C]osimertinib ^s		X	X		X		
Venous blood sampling for [¹¹ C]osimertinib radioactivity and metabolites ^{r,t}		X	X		X		
[¹¹ C]osimertinib administration		X	X		X		
PET examination		X ^{e,t}	X ^{e,t}		X ^{e,t}		
Osimertinib oral administration 80mg once daily ^u				X (continuous daily administration)			
Adverse event review (AEs and SAEs)	X ^v	X ^v	X ^v	X ^v	X ^v		X ^{v,w,x}

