5.2.3 ECG

Twelve-lead ECGs will be obtained after the patient has been resting semi-supine for at least 10 minutes. All ECGs should be recorded with the patient in the same physical position. For each time point 3 ECG recordings should be taken at about 5 minute intervals. A standardised ECG machine should be used and the patient should be examined using the same machine throughout the study if possible.

After paper ECGs have been recorded, the Investigator or designated physician will review each of the ECGs and may refer to a local cardiologist if appropriate. A paper copy should be filed in the patient’s medical records. If an abnormal ECG finding at screening or baseline is considered to be clinically significant by the Investigator, it should be reported as a concurrent condition. For all ECGs details of rhythm, ECG intervals and an overall evaluation will be recorded.

ECG data will be collected digitally and will be transferred electronically for central analysis as described in the study specific ECG manual. The investigator may choose to perform a non-digital ECG at the time of the screening visit in order to identify patients eligible for study entry. If a non-digital ECG is performed at the screening visit it cannot subsequently be used as a baseline recording, in this situation an ECG will need to be collected on the baseline visit in digital form.

Heart rate, PR, R-R, QRS and QT intervals will be determined and reviewed by an external cardiologist.

If there is a clinically significant abnormal ECG finding during the treatment period, this should be recorded on the AE pCRF, according to standard AE collection and reporting processes (see Section 6.3.6). A 28-day follow-up assessment will be required if an on-treatment assessment was abnormal at the time of discontinuation of the IP or study, to confirm reversibility of the abnormality. Information on osimertinib dose reduction for QTc interval prolongation is detailed in Section 6.8.4.

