6.8.4 QTc prolongation

In light of the potential for QT changes associated with osimertinib, electrolyte abnormalities (hypokalemia, hypomagnesemia, hypocalcemia) must be corrected to be within normal ranges prior to first dose and electrolyte levels monitored during study treatment

Refer to Table 4 above. Patients with QTcF prolongation to >500 msec should have study treatment interrupted and regular ECGs performed until resolution to <481 msec, or recovery to baseline if baseline QTcF is ≥ 481 msec and then restarted at a reduced dose of 40mg, or 80mg at the discretion of the investigator. If the toxicity does not resolve to \leq grade 1 within 21 days the patient will be permanently withdrawn from study treatment. The Investigator or designated physician should review each ECG prior to discharge and may refer to a local cardiologist if appropriate for immediate management of the patient.

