3.3 Safety and tolerability variables

Safety and tolerability will be assessed by:

- Assessment of adverse events (AEs), graded by Common Terminology Criteria for Adverse Events (CTCAE) (v4.03)
- Physical examination
- Vital signs (including blood pressure [BP], pulse rate, body temperature, and weight)
- Standard 12 lead electrocardiograms (ECGs)
- Evaluation of laboratory parameters (clinical chemistry, coagulation, haematology and urine analysis)
- Echocardiogram/multiple gated acquisition scan (MUGA)
- Concomitant medications

Adverse events will be classified according to the terminology of Medical Dictionary for Regulatory Activities (MedDRA), Version 21.0 or higher (preferred term and system organ class [SOC]).

Adverse events reported before any administration of osimertinib will be listed only and be referred to as “pre-treatment”. Similarly, AEs reported before any administration of osimertinib that continue after the first administration without worsening will also be classified as “pre-treatment”.

A treatment emergent AE (TEAE) will be defined as any AE with start date and time on or after the first IV dosing of osimertinib in imaging phase up to 30 days after their last study treatment administration or immediately before initiation of any other cancer therapy, whichever occurs first.

For laboratory data, vital signs and ECG data, baseline is defined as the latest result obtained prior to the first IV dose of osimertinib in the imaging phase.

For all safety data, an on-treatment period is from after the first IV dose of osimertinib in the imaging phase, up to and including the follow-up visit.

Patients not participating in the continued access phase or who discontinue treatment during the imaging phase will return to the clinic for follow-up assessments 30 days (± 7 days) after their last administration of osimertinib in the imaging phase. If the patient’s last administration of osimertinib is in the continued access phase, the patient will be contacted 30 days after their last administration of osimertinib to follow up on any existing AEs/SAEs and monitor for new AEs/SAEs that may be related to the IP, and record any sudden deaths of unknown cause. This follow-up assessment will serve as the end-of study assessment for a patient.

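### For patients who stop osimertinib in or at the end of the imaging phase, the overall ECG shift table can replace an abnormal on-drug ECG with an off-drug recovery ECG

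*SAP*

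**What the plan says.** Four rules meet here.

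- **Table rule (SAP 4.3.3).** "Overall ECG evaluation will be summarised using shift tables summarising the change from baseline to last on-treatment observation across all patients". The section sets no on-drug cut-off for this table and does not exclude unscheduled tracings.
- **Period (SAP 3.3).** The rule covers every type of safety measurement: "an on-treatment period is from after the first IV dose of osimertinib in the imaging phase, up to and including the follow-up visit". For patients who do not enter continued access, or who stop during the imaging phase, that visit consists of "follow-up assessments 30 days (± 7 days) after their last administration of osimertinib in the imaging phase". The starting point of the shift is also in SAP 3.3: "baseline is defined as the latest result obtained prior to the first IV dose of osimertinib in the imaging phase".
- **Conditional ECG (Protocol 5.2.3).** "A 28-day follow-up assessment will be required if an on-treatment assessment was abnormal at the time of discontinuation of the IP or study". Its stated purpose is "to confirm reversibility of the abnormality".
- **Routine schedule (Protocol Table 1).** The row "Resting standard 12-lead ECG" is marked at screening, PET1, PET2, Clinical Visit 2 and the PET3 visit. It has no mark at follow-up, whereas the vital-sign and laboratory rows do.

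**The concern.** A shift table headed last on-treatment is read as showing how patients looked on the drug. Here its final value can come from an ECG taken about four weeks after the drug was stopped, whose purpose is to see whether an abnormality has gone away. That ECG is required only in patients who were abnormal at stopping. Patients who were normal at stopping have no planned later tracing, so their on-drug result stands.

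The replacement is therefore selective, and it works towards no effect. ECG is a named measure under the safety objective, and this is the only planned summary of the overall ECG evaluation. A reader of the table alone could conclude that nobody shifted to abnormal when someone did so on drug and later recovered.

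**Working it through.** The documents state no figure for this table, so there is none to reproduce. The check is one of timing and counting.

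**Step 1. Does the 28-day ECG fall inside the on-treatment period?** Inputs: follow-up visit at 30 ± 7 days (SAP 3.3) and ECG at 28 days (Protocol 5.2.3). I assume both are counted from the last imaging-phase dose.

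- Earliest visit: 30 − 7 = day 23. Latest visit: 30 + 7 = day 37.
- 23 ≤ 28 ≤ 37, so the two can coincide.
- A day-28 ECG is on or before the visit if the visit falls on days 28 to 37, which is 37 − 28 + 1 = 10 of the 37 − 23 + 1 = 15 permitted days. On the other 5 (days 23 to 27), an ECG done exactly at day 28 comes after the visit and is outside the period. These are counts of days, not probabilities. The documents do not say whether the two are done together.

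**Step 2. Which ECG is last under the SAP rule?**

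| Patient | Last planned ECG in the period | State when taken |
|---|---|---|
| Goes from PET3 directly into continued access | PET3 visit (no ECG data collected afterwards) | on drug |
| Stops, ECG normal at stopping | last ECG at or before stopping | on drug |
| Stops, ECG abnormal at stopping, 28-day ECG on or before the visit | 28-day ECG | off drug |
| Stops, ECG abnormal at stopping, 28-day ECG after the visit | last ECG at or before stopping | on drug |

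Only the third row is changed, and it consists entirely of patients who were abnormal at stopping.

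**Step 3. Effect on the normal-to-abnormal cell.** I assume the overall evaluation is classed as normal or abnormal. Let N be the patients in the table, k the third-row patients who were normal at baseline, and r the number of those k who are normal again at the 28-day ECG. Shifts in the other rows are the same under both rules and cancel.

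- Ending at the last on-drug ECG, these patients contribute k/N.
- Under the SAP rule, they contribute (k − r)/N.
- Difference: r/N, which is never negative.

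N = 12 is the planned number treated (SAP 1.3) and N = 8 the planned minimum completing. The values of k and r are illustrations, since the documents give no abnormality or recovery rate.

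| N | k | r | Last on-drug ECG | SAP rule |
|---|---|---|---|---|
| 12 | 1 | 1 | 1/12 = 8.3% | 0/12 = 0% |
| 12 | 2 | 1 | 2/12 = 16.7% | 1/12 = 8.3% |
| 12 | 3 | 3 | 3/12 = 25.0% | 0/12 = 0% |
| 12 | 3 | 0 | 3/12 = 25.0% | 3/12 = 25.0% |
| 8 | 1 | 1 | 1/8 = 12.5% | 0/8 = 0% |

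Each recovered patient removes 1/12 = 8.3 percentage points, or 1/8 = 12.5 with the smaller denominator. With r = 0 the two rules agree.

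The trigger in Protocol 5.2.3 is any abnormal tracing at stopping, not a new one. Patients already abnormal at baseline are therefore outside k: they are not normal-to-abnormal shifts under either rule.

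**The case against.** The strongest reply is that little depends on this table. The study is descriptive and has about 12 patients. ECG variables are listed by patient, and heart rate, RR, PR, QRS, QT and QTcF are summarised as observed values and changes at scheduled time points. QTcF outliers are counted at any assessment after the first microdose, so a later normal tracing cannot erase one. Clinically significant findings also go to the adverse event form. Most of this stands, and it sets the severity. The adverse event route is only a partial backstop: Protocol 6.3.6 limits reporting of deteriorations in protocol-mandated tests to those that are serious or lead to discontinuation, on the ground that the results will be summarised elsewhere.

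A reader might infer more than the documents support:

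- **That a QT signal would be hidden, or that all conduction findings depend on this table.** The QTcF outlier counts and the PR and QRS summaries show otherwise. Only the overall evaluation depends on the shift table.
- **That the table would show only abnormalities that failed to recover.** Patients who pass directly into continued access keep their PET3 ECG whatever happens later.
- **That ECGs during a dose interruption do the same.** Protocol 6.8.4 says that patients with QTcF above 500 msec "should have study treatment interrupted and regular ECGs performed until resolution to <481 msec". But Protocol 6.8 introduces its toxicity-management text as guidance for continued access, where no ECG data are collected. A patient who interrupts in the imaging phase, resumes and reaches PET3 has a later on-drug ECG. The route matters only for someone who never resumes before follow-up.
- **That the 28-day ECG always counts as on-treatment.** It does not if the visit falls on days 23 to 27 and the ECG is done afterwards.

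**Conclusion.** Wrong as written, with minor severity: one descriptive safety table is affected. The defect follows from the rules read together. An ECG meant to show recovery, and required only in patients abnormal at stopping, can serve as the end of an on-treatment shift.

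It is confined to patients who stop osimertinib in or at the end of the imaging phase and whose 28-day ECG is done on or before the follow-up visit. In that group, each patient who was normal at baseline, abnormal at stopping and recovered lowers the count of shifts to abnormal by one (8.3 percentage points of 12). The total is unknown and may be zero. The direction rests on the planned ECGs only: an unscheduled later tracing in a patient who was normal at stopping is not considered here.

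The documents do not support a general objection to the SAP 3.3 period. Laboratory and vital-sign data have routine follow-up assessments in Table 1 and are summarised by scheduled time point, so the selective replacement does not arise there.

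**What to change.** In SAP 4.3.3, define the end of the shift as the last overall ECG evaluation obtained while the patient is taking osimertinib in the imaging phase, meaning on or before discontinuation and including the ECG at discontinuation. The baseline definition stays as it is. List or summarise the 28-day ECG separately, labelled as recovery.

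The on-treatment definition in SAP 3.3 can stay for laboratory and vital-sign data. Moving to the worst on-drug evaluation is an option some would prefer, but it is not needed to remove this problem.

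The cost is a sentence or two of SAP text and one table specification, settled before database lock. No new data or procedures are needed.
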